## Statistical Analyses

Assuming that there are no ordering or period effects in the trial, we will use a paired t-test to compare ratings of anxiety during the impromptu speech task after BHV-0223 vs. placebo treatment. Given a sample size of 20 subjects, assuming a one-sided  $\alpha=0.1$ , we would have 80% power to detect a treatment effect size=0.5 or greater. As a comparison previous studies of benzodiazepines have demonstrated an effect size of at least 0.9 on similar speech paradigms (32). Our primary measure will be the VAS-anxiety after the impromptu speech task (BHV-0223 compared to placebo). As additional secondary measures we will collect (1) subject ratings of speech performance, self-statements during public speaking (SSPS) and specific anxiety symptoms during speech (STAI); (2) clinical ratings of speech performance; (3) duration of speech; (4) assessments of cognition – (DSST and 15 word recall) and 5) side-effects.

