- Each subject will be given BHV-0223 (or placebo) under double-blind conditions 1-hour before performing the impromptu speech task on 2 separate study days.
- There will be a 2 to 10 day washout period between study days.
- There will be a final Follow-up visit 2 to 10 days later to do blood work and complete physical exam.

Overview:

We propose conducting a double-blind, placebo controlled crossover study examining the effects of BHV-0223 on public speaking anxiety. Twenty subjects with DSM-5 defined social anxiety disorder and clinically significant public speaking anxiety on the Impromptu Speech Task will be enrolled in a challenge study. Subjects will be given BHV-0223 (or placebo) under double-blind crossover conditions 1 hour prior to performing each of 2 impromptu speech tasks. The two study days involving BHV-0223 (or placebo) administration and impromptu speech task will be separated by 2 to 10 days to allow for medication washout. There will be a final follow-up visit 2 to 10 days later to perform a complete Physical exam and do follow-up liver function testing and a Complete Blood Count. Our primary outcome will examine BHV-0223's effects (compared to placebo) on self-rated anxiety during the impromptu speech task. We will also collect physiological measures of anxiety, clinician-rated measures of anxiety, and measures of speech performance as secondary outcomes.

Screening:

A baseline screening assessment to determine study eligibility, clinical ratings, and physical health will be conducted at least one week prior to the challenge study.

*Medical Assessments*

During the screening visit, vital signs (BP, HR: supine, standing X 2-3 min), physical exam (including a comprehensive exam of the oral cavity see Appendix 1), and clinical laboratory tests (i.e. CBC with differential, complete metabolic panel (CMP) (including electrolytes, LFTs, BUN, creatinine and glucose), TFTs, urine drug screen, and routine urinalysis) will be completed. A pregnancy test will be given to all females of childbearing age enrolled in the study prior to participating in the study sessions. We will also perform a visual inspection of the mouth cavity to assess local tolerability before and 1 hour after administering study medication on each study day (please see appendix document for further details).

*Psychiatric Assessments*

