The SCID (Structured Clinical Interview for DSM disorders) on the screening day to verify presence of social anxiety disorder and the absence of other psychiatric conditions (psychotic disorders, current substance abuse/dependence etc.). The *Liebowitz Social Anxiety Scale (LSAS)* will be administered to determine that public speaking anxiety symptoms are significant enough for inclusion in the trial. The LSAS is a rating scale that assesses SAD severity (21) and a 5-item subscale rates public speaking fear (22). Psychiatric rating scales examining the severity of anxiety (*Hamilton Anxiety Rating Scale (HAM-A)* (23)) and depressive symptoms *Hamilton Depression Rating Scale (HAM-D)* (24) will also be administered. Per FDA guidelines, suicidal ideation and behavior will be monitored using the C-SSRS(25) at screening and on every visit day.

Intervention:

Subjects will be given BHV-0223 35mg or placebo in a random order as assigned through the CMHC pharmacy with a 2 to 10 day separation between task days. Randomization will be performed by the CMHC pharmacy. The identity of the treatments will be concealed by the use of study drugs that are identical in packaging, labeling, schedule of administration and appearance. Placebo and study drug will be prepared in a like fashion in the CMHC pharmacy. Unblinding of a specific patient's randomization assignment will only occur during the study in the case of specific patient emergencies.

BHV-0223 is a sublingual, oral-disintegrating tablet containing 35mg of riluzole drug substance. BHV-0223 35mg tablets have shown bioequivalence to riluzole 50mg administered orally (please see PIND 128411 for further details). The half-life of BHV-0223 is just under 8 hours. Riluzole is a member of the benzothiazole class of medications. Chemically, its molecular formula is  $C_8H_5F_3N_2OS$  and its molecular weight is 234.2. The efficacy of riluzole in the treatment of ALS was established in two well-controlled studies. Patients randomized to treatment with riluzole showed longer time to tracheotomy or death compared to those treated with placebo. The recommended dose of riluzole in the treatment of ALS is 50mg taken every 12 hours (at least an hour before, or two hours after, a meal to avoid food-related decreases in bioavailability). Riluzole's mechanism of action in the treatment of ALS is unknown but thought to be due to its down-modulation of glutamatergic neurotransmission.

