### Assessments

#### *Impromptu Speech Behavioral Assessment Test*

The impromptu speech BAT will be performed 1 hour after the subject receives study medication as outlined in the table below (26-28). Participants will be asked to speak about pre-determined topics for 10 minutes to a small audience of research staff

(27). Patients with more severe social anxiety symptoms are often not able to speak for the full 10 minutes and have shorter speech lengths when compared to those with less severe social anxiety symptoms (26-28). VAS-anxiety, State-Trait Anxiety Inventory and the Self-Statement during Speech Test (SSPS) (28) will be assessed before and after the speech. The Local Tolerability Assessment (Appendix 1) will be performed at screening, baseline, 1 hour after receiving the study medication and before discharge.

The Table below shows the assessment schedule for participants enrolling in the trial.

Measure	Screening	Challenge DAY 1					2-10 day washout period	Challenge DAY 2					2-10 days	Follow up visit
		Baseline	0	1h	2h	3h		Baseline	0	1h	2h	3h		
Local Tolerability Assessment	X	X		X		X		X		X		X		
Impromptu Speech Task				X					X					
VAS-anxiety	X	X	X	X	X	X		X	X	X	X	X		
VAS-speech performance				X					X					
SSPS		X		X				X	X					
STAI		X		X				X	X					
DSST		X		X				X	X					
Immediate and Delayed Word Recall		X		X				X	X					
Clinical-rated VAS-anxiety				X					X					
Clinician rated VAS-speech performance				X					X					
LSAS	X	X						X						
SCID	X													
C-SSRS	X					X						X		
Physical Exam with Vital signs (BP, HR: supine, standing X 2-3 min) and Visual exam of the oral cavity	X	X				X		X				X		X
Blood test	X													X
Urine Test	X	X						X						
EKG	X													
STUDY MEDICATION ADMINISTRATION			X						X					

The rating scales utilized in the trial are detailed in the table below. Ratings will be conducted by raters that are blinded to treatment assignment and will not be present during medication administration.

- RATING SCALES:**
- 1) *Visual Analog Scale (VAS) of Anxiety States:* The VAS includes scales for anxiety, drowsiness, high, irritability, anger, and sadness. These scales are 100 mm lines marked by participants at a point corresponding to the apparent intensity of the feeling state (0=none, to 100=most ever) (29). We will also use clinician-rated visual analogue scales to measure subject anxiety and speech performance during the Impromptu Speech Task.

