#### **7. Plan for reporting adverse events to co-investigators on the study, as appropriate the protocol's research monitor(s), and funding and regulatory agencies, and regulatory and decision-making bodies.**

For the current study, the following individuals, funding, and/or regulatory agencies will be notified (choose those that apply):

All Co-Investigators listed on the protocol.

Food and Drug Administration

The principal investigator ([name]) will conduct a review of all adverse events upon completion of every study subject. The principal investigator will evaluate the frequency and severity of the adverse events and determine if modifications to the protocol or consent form are required.

- d. For multi-site studies for which the Yale PI serves as the lead investigator: N/A
  - i. How will adverse events and unanticipated problems involving risks to subjects or others be reported, reviewed and managed?

- ii. What provisions are in place for management of interim results?
- iii. What will the multi-site process be for protocol modifications?

**12. Statistical Considerations:** Describe the statistical analyses that support the study design.

Assuming that there are no ordering or period effects in the trial, we will use a paired t-test to compare ratings of anxiety during the impromptu speech task after BHV-0223 vs. placebo treatment. Given a sample size of 20 subjects, assuming  $\alpha=0.05$ , we would have 80% power to detect a treatment effect size=0.58 or greater. As a comparison previous studies of benzodiazepines have demonstrated an effect size of at least 0.9 on similar speech paradigms (32). Our primary measure will be the VAS-anxiety after the impromptu speech task (BHV-0223 compared to placebo). As additional secondary measures we will collect (1) subject ratings of speech performance, self-statements during public speaking (SSPS) and specific anxiety symptoms during speech (STAI); (2) clinical ratings of speech performance; (3) duration of speech; (4) assessments of cognition – (DSST and 15 word recall) and 5) side-effects.

We additionally take an interim examination of the efficacy data at the trial after 10 subjects to evaluate the initial side-effects of the compound and to examine initial efficacy. We would consider a treatment effect size of less than 0 (BHV-0223 worsen anxiety during the impromptu speech task compared to placebo) as a rationale to stop the trial early.

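### The primary paired t-test assumes no period effect between two speeches and has no fallback; a shift costs power, and with unequal orders it also biases the realized contrast

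*Combined protocol and SAP*

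**What the plan says.** The primary analysis appears twice, in Section V.3 (Statistical Analyses) and Section V.12 (Statistical Considerations), with the same opening: "Assuming that there are no ordering or period effects in the trial, we will use a paired t-test to compare ratings of anxiety". Neither section includes a period or sequence term, a check of the assumption, or an alternative if it fails.

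The Overview in V.3 has subjects dosed "under double-blind crossover conditions 1 hour prior to performing each of 2 impromptu speech tasks", with 2 to 10 days between the two days. The Intervention text gives treatment "in a random order as assigned through the CMHC pharmacy". It does not mention blocking or equal numbers per order, and does not rule them out. The primary measure is VAS-anxiety after the speech. The Assessments text adds that "VAS-anxiety, State-Trait Anxiety Inventory and the Self-Statement during Speech Test (SSPS) (28) will be assessed before and after the speech", and the schedule shows VAS-anxiety at Baseline on both challenge days. The analysis gives that baseline no role.

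**The concern.** A second speech to an audience, a few days after the first, may provoke less anxiety (habituation) or more (sensitization). The documents give no evidence either way. The washout does not settle it: with a half-life of just under 8 hours, 48 hours is at least 6 half-lives, which deals with residual drug but not with having done the task before.

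If the shift is not zero, two things follow. It inflates the SD of the paired differences, so the test loses power even with perfectly balanced orders. If the orders are unequal, by chance or through drop-out, part of the shift is counted as drug effect. Deciding on a period term after seeing the data would then be a post hoc change to the primary analysis of a 20-subject trial.

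**Working it through.** **Inputs.** From V.3: "Given a sample size of 20 subjects", "assuming a one-sided" alpha of 0.1, and "we would have 80% power to detect a treatment effect size=0.5 or greater". From V.12: alpha 0.05 with sidedness not given, and "we would have 80% power to detect a treatment effect size=0.58 or greater". Assumed here: effect size means the mean paired difference divided by the SD of paired differences within an order (the plan does not define it), and the period shift P, in the same SD units, ranges from 0 to 0.75.

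**The plan's own figure.** With no period effect the paired t has 19 df, critical value 1.328 and noncentrality 0.5 × √20 = 2.236. Exact power is 81.7%, so the stated 80% is right on its own inputs. The V.12 figure reproduces at one-sided 0.05 (80.4%) but not at two-sided 0.05 (69.2%).

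**Model with a shift.** D_i = τ + P·s_i + e_i, where e_i ~ N(0,1) and s_i = +1 or −1 by order.

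- Paired t: the mean of D has expectation τ + P(n₁−n₂)/n. The sample variance has expectation 1 + 4P²n₁n₂/[n(n−1)].
- Period-adjusted: the average of the two order means, with variance (1/n₁+1/n₂)/4 and n−2 df. P cancels.

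At 10/10 and P=0.5 the paired estimate is unbiased, but the estimated variance averages 1 + 0.25 × 400/380 = 1.263. The SD is therefore about 12% too large.

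**Balanced orders, 10/10, one-sided 0.10, effect 0.5 (simulated):**

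| P | Paired power | Adjusted power | Paired type I error |
|---|---|---|---|
| 0 | 82% | 82% | 10% |
| 0.25 | 81% | 82% | 9% |
| 0.3 | 80% | 82% | 9% |
| 0.5 | 77% | 82% | 8% |
| 0.75 | 71% | 82% | 5% |

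Power crosses 80% at about P=0.3.

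**Unequal orders.** Bias is P(n₁−n₂)/n. The two type I error figures are for a bias favouring drug and a bias favouring placebo. The adjusted test holds 10% in every row.

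| Split | P | Bias (SD) | Paired type I error |
|---|---|---|---|
| 11/9 | 0.5 | 0.5×2/20 = 0.05 | 11% or 5% |
| 12/8 | 0.5 | 0.5×4/20 = 0.10 | 16% or 3% |
| 13/7 | 0.25 | 0.25×6/20 = 0.075 | 16% or 5% |
| 13/7 | 0.5 | 0.5×6/20 = 0.15 | 22% or 2% |
| 10/8 (drop-out) | 0.5 | 0.5×2/18 = 0.06 | 11% or 5% |
| 10/7 (drop-out) | 0.5 | 0.5×3/17 = 0.09 | 14% or 4% |

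If order were assigned by simple randomization, 12/8 or worse has probability 50% and 13/7 or worse 26%.

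**Averaged over simple randomization.** Type I error is 10% for both tests. Paired power is 82%, 80%, 75% and 68% at P = 0, 0.25, 0.5 and 0.75, against 80% adjusted throughout.

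**V.12 inputs, effect 0.58, 10/10.** At P = 0.25, 0.5 and 0.75 paired power is 79%, 74% and 66% against 80% adjusted if alpha is one-sided, or 67%, 60% and 49% against 69% if two-sided. The gap between 80% and 69% comes from the unstated sidedness, which is a separate matter.

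**The case against.** Every loss depends on an assumed P. At P=0.25 with balanced orders paired power still meets the stated 80%, and P=0.5 is a shift as large as the drug effect being sought. If the drug effect were 0.9, the benzodiazepine figure the plan cites for comparison, paired power at 10/10 would be 98% even at P=1.0. Randomizing the order protects the estimate and the error rate on average, so the bias exists only conditional on the realized split. The pharmacy may in fact block to 10/10, and then a shift makes the paired test conservative, so a positive result would be safer than nominal. Under simple randomization 74% of trials would be 12/8 or closer, so 13/7 is not typical. Finally, a period term removes only an additive shift. If the first day's treatment changes how the second speech is experienced, it does not help.

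All of this is true, and it limits the size of the problem. It does not remove it. P=0 is also an assumption, and the plan's primary test depends on it. The trial will have one split, and its result will be read at that split. Balance would cure the bias but not the lost power. The plan targets 0.5, not 0.9. The limit to an additive shift applies to the remedy, and the paired t-test does no better there.

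**Conclusion.** The concern holds. The primary analysis relies on an assumption that the plan itself names, does not support and does not cover if it fails. The consequence is small for a shift of 0.25 SD with balanced orders (about 1 point of power). It becomes material from about 0.5 SD: 4 to 5 points at 10/10, and 7 points averaged over simple randomization (82% to 75%). With unequal orders, the false-positive rate for the realized split moves away from 10% in a direction nobody can know in advance, up to 22% or down to 2% at 13/7 and P=0.5. Over repeated simple randomization there is no bias and no inflation of type I error.

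These figures rest on an assumed P, an additive shift, normal differences, and effect size read on the paired-difference scale. The 13/7 probability also assumes simple randomization, and the drop-out rows assume losses from one order only. Because the size of P is unknown, this is a change that should be made, with medium confidence in how much it will matter.

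**What to change.** In V.3 and V.12, replace the paired t-test with the period-adjusted crossover contrast of post-speech VAS-anxiety: treatment, period and sequence as fixed effects and subject as random, or the equivalent two-sequence t-test on period differences. Specify it outright, not conditional on a preliminary test for a period effect. State that the pharmacy randomizes order in blocks to 10/10. The same model can serve DSST and word recall for consistency, although the documents give no evidence of practice effects there.

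Optional: add the within-subject difference in same-day pre-dose Baseline VAS-anxiety as a covariate, not as a change score. Leaving it out causes no bias. Including it gives power of 80%, 83%, 88% and 95% at assumed correlations of 0, 0.3, 0.5 and 0.7, so it costs about 2 points if uncorrelated and breaks even near 0.25.

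The cost is protocol wording and a few lines of code, with no new data or visits. If there is truly no period effect, the period term costs under 0.1 point of power at 10/10, about 3 points at 13/7 (79% against 82%), about 5 at 14/6 (76%), and about 2 averaged over simple randomization. Blocking keeps the cost near zero.

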### **Ratings and Speech Task**

Patients may find the battery of behavioral ratings tedious. Additionally, the subjects are likely to find the speech task anxiety provoking. Subjects may (and often do) discontinue the speech task at any point if they feel excessively uncomfortable. We have used this speech tasks in previous task without significant adverse events.

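### The primary paired t-test drops any subject rated on only one challenge day, and the target of 20 leaves no room for such losses; a mixed model would keep them at almost no cost

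*Combined protocol and SAP*

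**What the plan says.** Section V.3 (Research Plan, Statistical Analyses) and Section V.12 (Statistical Considerations) give the same primary analysis: "we will use a paired t-test to compare ratings of anxiety during the impromptu speech task after BHV-0223 vs. placebo treatment". Both introduce it with the condition "Assuming that there are no ordering or period effects in the trial". The primary measure is the self-rated VAS-anxiety after the speech.

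Section V.3 sizes the trial as follows: "Given a sample size of 20 subjects", with a one-sided alpha of 0.10, "we would have 80% power to detect a treatment effect size=0.5 or greater". Section VII.1 sets the enrolment target at 20, the same number.

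Treatment order is random, and the two challenge days are 2 to 10 days apart. The text available for review gives no expected dropout rate, replacement rule, analysis set, missing-data method or sensitivity analysis.

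On tolerability of the task, Section V.9 (Ratings and Speech Task) says that "the subjects are likely to find the speech task anxiety provoking" and that subjects often stop the speech early. Section V.3 (Assessments) says that more severe patients often cannot speak for the full 10 minutes.

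**The concern.** The test statistic is built from within-subject differences, so a subject with one rating has no difference to contribute. That rating was nevertheless obtained after randomisation and dosing, and it carries information. With 20 subjects, each one lost is 5% of the sample.

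Two things are at stake. The first is power, because there is no margin above 20. The second is bias. If the decision to return depends on how Day 1 went, the completers are a selected group. The selection then acts differently on those who had drug first and those who had placebo first.

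**Working it through.** **1. The plan's own figure.** Inputs from Section V.3: n = 20, standardised paired effect d = 0.5, one-sided alpha 0.10. Power = P(T > t(0.90; n−1)), where T is noncentral t with n−1 degrees of freedom and noncentrality d√n = 0.5 × √20 = 2.24. The result is 81.7%, which agrees with the stated 80%. Section V.12 gives a different alpha (0.05, sidedness not stated) and states "we would have 80% power to detect a treatment effect size=0.58 or greater". That figure reproduces only if one-sided (80.4%; two-sided 69.2%). The conflict is a separate matter to reconcile, and the figures below use the V.3 version.

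**2. Power by number of complete pairs** (same formula):

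| Pairs | 20 | 19 | 18 | 17 | 16 | 14 |
|---|---|---|---|---|---|---|
| Power | 81.7% | 80.2% | 78.5% | 76.6% | 74.6% | 70.2% |

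Two losses cost 81.7 − 78.5 = 3.2 points. Four cost 81.7 − 74.6 = 7.1 points.

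**3. Loss driven by Day 1 anxiety, same rule after drug and placebo.** Neither the dropout rate nor the within-subject correlation ρ is in the documents, so both are assumed over a range. The simulation used 20 subjects, 10 per order, d = 0.5, one-sided 0.10 and a logistic loss model with slope 2 per SD of Day 1 anxiety. Completers-only paired t was compared with a REML random-intercept model on all ratings. Entries are power, paired / mixed:

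| Lost | ρ = 0.3 | ρ = 0.5 | ρ = 0.7 |
|---|---|---|---|
| 10% | 76.4 / 79.5 | 76.7 / 78.8 | 77.9 / 78.9 |
| 20% | 72.6 / 77.4 | 73.3 / 76.3 | 74.1 / 76.0 |
| 30% | 68.5 / 75.3 | 69.0 / 73.3 | 69.3 / 71.9 |

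The mixed model recovers between 1.0 point (10%, ρ = 0.7) and 6.8 points (30%, ρ = 0.3). It does not restore 81.7%. At 20% and ρ = 0.5, the paired test is 81.7 − 73.3 = 8.4 points short, the model regains 3.0, and 5.4 remain lost.

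The bias is small here because random order makes it run in opposite directions. At ρ = 0.5 and 20% loss, drug-first completers show −0.60 and placebo-first completers −0.34, against a true −0.50. The simple average is −0.47. Over the grid, completers keep 94–98% of the effect, or 91–96% if everyone above an anxiety threshold leaves. The mixed model keeps 99.5–100.3%. With no drug effect, the paired test rejects 9.5–10.0% of the time at a nominal 10%.

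**4. Loss in one order only.** Assumption: 80% non-return above the placebo 70th percentile of Day 1 anxiety, true effect 0.50, ρ 0.3–0.7.

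- Only placebo-first subjects leave: the paired estimate is 0.41–0.43 with power 67–69%; the mixed model gives 0.49–0.50 with 77–80%.
- Only drug-first subjects leave: the paired estimate is about 0.54–0.56; the mixed model gives 0.49–0.50. With no drug effect, the paired test rejects about 15–17% of the time at a nominal 10%.

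Other runs at 10–20% loss gave a similar pattern: 79–91% of the true effect for placebo-first loss and 109–122% for drug-first loss.

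**5. Random loss and no loss.** With 20% lost at random there is no bias. Power is 74.0 / 77.2, 74.5 / 76.8 and 75.1 / 76.5 at ρ = 0.3, 0.5 and 0.7, a gain of 1.4 to 3.2 points. With all 20 complete, the two analyses have the same power.

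**6. Why period belongs in the model.** Every unpaired rating comes from Day 1. With an assumed Day 2 fall of 0.3 SD and anxiety-driven loss, a mixed model without a period term gives 0.48 instead of 0.50, and the paired t gives 0.45–0.46. The power figures above come from a model without that term.

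**The case against.** A reader might infer that the most anxious subjects will fail to return, so that the estimate is necessarily pulled toward zero. The documents do not support that. Their remarks on discomfort concern stopping the speech, not missing the second visit. Stopping early need not lose the primary rating, because VAS-anxiety is taken repeatedly on each day and speech duration is a separate secondary measure. Several features favour retention: the short gap, payment of $100 per challenge day, and earlier use of the task without significant adverse events. Nor is the direction fixed. Loss twice as likely after drug gives 102–105% of the true effect.

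It is also fair to say that the size is modest under symmetric loss. A bias of 0.02–0.04 SD compares with a standard error of 1/√16 = 0.25 SD with 16 pairs, at most about one sixth of it. Most of the lost power comes from the missing observations themselves. The paired t-test is a standard crossover analysis, and this is a proof-of-concept trial.

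All of this stands, and it limits the point to an inexpensive improvement. It does not remove the point: the test discards single-day subjects, the target has no margin, and loss in one order can distort both the estimate and the error rate.

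**Conclusion.** The concern holds in a conditional form. The paired t-test drops every subject with one rated day, and enrolment of 20 leaves no allowance for that. The cost is zero if everyone completes. With 10–30% loss related to Day 1 anxiety equally after both treatments, it is about 1–7 points of recoverable power and a 2–9% attenuation. Only loss concentrated in one order produces a material bias: downward after placebo, or upward with an inflated error rate after drug. A claim that the result will be biased toward the null goes beyond the documents.

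These sizes rest on assumed dropout, assumed correlations of 0.3–0.7, normal outcomes, and loss explained by the Day 1 rating. If return depends on something unrecorded, the mixed model is not protected either.

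**What to change.** In Sections V.3 and V.12, make the primary analysis a linear mixed model on the available post-speech VAS-anxiety ratings of all randomised subjects. Use treatment and period as fixed effects, subject as a random effect and small-sample degrees of freedom, at the same sidedness and alpha as the reconciled power statement. Keep the paired t-test on complete pairs as a sensitivity analysis.

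The change is about two sentences and uses data already collected. With all 20 pairs complete and 10 per order, the treatment estimate equals the paired mean difference, and the period term costs about one degree of freedom (18 instead of 19). Otherwise the cost is slightly more analysis work. The model does not replace lost observations, so the text should also say whether 20 means subjects enrolled or subjects completing both days.

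### The pre-dose VAS-anxiety rating taken on both challenge days is not used in the primary analysis; prespecifying it as a covariate would be a cheap improvement, not the correction of an error.

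*Combined protocol and SAP*

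**What the plan says.** Section V, item 3, Statistical Analyses, names the test: "we will use a paired t-test to compare ratings of anxiety during the impromptu speech task after BHV-0223 vs. placebo treatment". It names the outcome as well: "Our primary measure will be the VAS-anxiety after the impromptu speech task (BHV-0223 compared to placebo". Item 12 of Section V, Statistical Considerations, repeats both. Neither place mentions a covariate, a change score or a period term, and both assume that there is no order or period effect.

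The schedule table under Assessments in Section V, item 3, has this row: "VAS-anxiety X X X X X X X X X X X". Its marks include the Baseline column of Challenge Day 1 and of Challenge Day 2. Study medication is marked in the separate 0 column, so the Baseline rating precedes dosing.

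The text above the table adds that "VAS-anxiety, State-Trait Anxiety Inventory and the Self-Statement during Speech Test (SSPS) (28) will be assessed before and after the speech". That sentence does not identify the pre-dose rating. The speech comes 1 hour after dosing, so a rating taken just before it may already carry a drug effect.

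The two power statements differ. Statistical Analyses starts from "Given a sample size of 20 subjects, assuming a one-sided" alpha of 0.1 and concludes "we would have 80% power to detect a treatment effect size=0.5 or greater". Statistical Considerations uses alpha 0.05 without stating sidedness and concludes "we would have 80% power to detect a treatment effect size=0.58 or greater".

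**The concern.** A paired test removes stable differences between people. It does not remove variation from one day to another within a person, and that variation is its whole error term. The two challenge days are 2 to 10 days apart, and a subject may arrive more anxious on one than on the other. If that difference carries through to the speech rating, the pre-dose VAS (same scale, same person, same day) would explain part of the error. The test as written cannot use it.

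The enrollment target of 20 is also the number in both power statements, so the trial has no slack. A covariate that is already being collected would add precision without new visits or data. If adjustment is wanted, it has to be written down before unblinding; added later, it would look driven by the data.

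**Working it through.** **Inputs from the documents.** n = 20; effect size d = 0.5 with one-sided alpha 0.10 (Statistical Analyses); d = 0.58 with alpha 0.05, sidedness not stated (Statistical Considerations). I take d as the mean paired difference divided by the SD of paired differences.

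**Assumed input.** r is the correlation between the within-subject difference in pre-dose VAS and the within-subject difference in post-speech VAS. The documents give no SD and no correlation, so r runs from 0 to 0.7.

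**Step 1: reproduce the plan's figure.** Power is the probability that a noncentral t with n − 1 degrees of freedom and noncentrality d√n exceeds the critical value.
- d = 0.5, one-sided 0.10: noncentrality 0.5 × √20 = 2.236, 19 df, critical value 1.328, power **81.7%**. The stated 80% reproduces.
- d = 0.58, alpha 0.05: noncentrality 0.58 × √20 = 2.594. Power is **80.4%** one-sided (critical value 1.729) and **69.2%** two-sided (2.093). The stated 80% reproduces only if the test is one-sided.

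**Step 2: adjust for the pre-dose difference.** Regress the post-speech difference on the pre-dose difference. The intercept is the treatment effect. Relative to the paired t-test, its variance is multiplied on average by

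f = (1 − r²) × (1 + 1/(n − 3)) = (1 − r²) × 18/17,

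where the second factor is the price of estimating the slope. Degrees of freedom fall to 18 and the noncentrality becomes d√(n/f). For r = 0.5, f = 0.75 × 1.059 = 0.794, and at d = 0.5 the noncentrality is 2.236/√0.794 = 2.509.

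| r (assumed) | f | d=0.5, one-sided 0.10 | d=0.58, one-sided 0.05 | d=0.58, two-sided 0.05 |
|---|---|---|---|---|
| Unadjusted | 1 | 81.7% | 80.4% | 69.2% |
| 0 | 1.059 | 80.0% | 78.2% | 66.4% |
| 0.3 | 0.964 | 82.7% | 81.5% | 70.5% |
| 0.5 | 0.794 | 87.9% | 87.6% | 78.6% |
| 0.7 | 0.540 | 95.4% | 96.0% | 91.6% |

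Simulation, with 40,000 trials per value of r, agrees to within about half a percentage point.

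**Step 3: break-even.** On variance alone, f = 1 when r² = 1/18, so r = 0.236. Allowing for the lost degree of freedom, power is equal at r of about 0.24 for d = 0.5, and at 0.24 to 0.25 for d = 0.58.

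**Step 4: equivalent sample size at r = 0.5.** An unadjusted paired t-test with n = 25, d = 0.5 and one-sided 0.10 has 88.0% power, against 87.9% adjusted with 20. The gain is therefore like having about 25 subjects. The shortcut 20/(1 − r²) = 26.7 leaves out the cost of the slope and is too generous.

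**Step 5: why not a change score.** If the pre-dose and post-speech differences are equally variable, subtracting the baseline multiplies the variance by 2 − 2r. At d = 0.5, one-sided 0.10, power is 60.4% at r = 0, 71.5% at r = 0.3 and 81.7% at r = 0.5. It falls below the plain paired t-test whenever r is under 0.5.

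**The case against.** The strongest objection is that nothing is broken. Treatment order is random, and chance differences in pre-dose anxiety between drug and placebo days are already part of the paired t-test's standard error. The test is valid under the plan's stated assumption, its power reproduces, and the trial calls itself a proof-of-concept study. All of this stands.

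The benefit is also unproven, and that stands too. Pairing has already taken out stable anxiety level, so only day-specific variation can help. Suppose, as an assumption, that ratings of the same kind correlate 0.6 across the two days at equal SDs. A same-day pre-dose to post-speech correlation of 0.5 with a cross-day correlation of 0.4 then gives r = (0.5 − 0.4)/0.4 = 0.25, which is barely break-even. If the cross-day correlation is also 0.5, r = 0. Nothing in the documents shows how large day-to-day swings are, or that pre-dose VAS predicts VAS after a provoked speech.

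Two stronger readings are tempting. A reader might infer that the plan certainly gives up precision; without r, the documents do not support that. A reader might also infer that an uncorrected chance imbalance biases the result. It does not. A one-standard-error imbalance moves the estimate by r/√20 SD, which is 0.11 SD at r = 0.5, but the test's error rate already allows for it.

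Day 2 Baseline also follows Day 1 dosing and speech. Drug carryover is unlikely, with a half-life just under 8 hours and at least 2 days between sessions. The experience of the first speech could still shift the second baseline, and that remains an assumption of the adjustment.

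**Conclusion.** The point holds as a cheap improvement. A pre-dose rating is scheduled on both challenge days and the primary analysis leaves it out. Under the Statistical Analyses inputs, adjustment changes power by between a loss of 1.7 points (r = 0) and a gain of 13.7 points (r = 0.7). The gain is 1.0 point at r = 0.3 and 6.2 points at r = 0.5. It pays only if r exceeds about 0.24.

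The downside is small and bounded, and the possible gain is useful at n = 20, so prespecifying the adjustment is reasonable. It is not the repair of an invalid test, and a definite loss of precision cannot be claimed. The figures rest on the assumed range for r, on 20 completers, and on no period term, which would cost one further degree of freedom. Quoting an adjusted power must wait until the two sections agree on alpha, sidedness and effect size.

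**What to change.** Prespecify one primary model: a linear regression of the within-subject post-speech VAS-anxiety difference (BHV-0223 minus placebo) on the within-subject difference in the Baseline-column VAS-anxiety. Define the treatment effect as the intercept, that is, the expected post-speech difference when the pre-dose difference is zero. Keep the unadjusted paired t-test as a supporting analysis.

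Use the Baseline column only. The 1h pre-speech rating is taken after dosing, and the timing of the rating in the 0 column relative to dosing is not stated. Do not use a simple change score. Do not offer a mixed model as an interchangeable alternative: with a random subject effect its baseline slope mixes between-subject and within-subject information, and it can give a different treatment estimate.

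First reconcile Statistical Analyses with Statistical Considerations on alpha, sidedness and effect size, then quote adjusted power with r stated as an assumption. The cost is analysis wording, one degree of freedom, and about 2 points of power if r is near zero (nearer 3 if the 0.05 test is two-sided: 69.2% to 66.4%). No new data or visits are needed.
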